**Product Fit and Performance:**

2. Product performance in terms of urine leaking (yes/no). We will calculate the percentage of leaks from loaded pants only. When comparing both products, Ninjama EU option should not be [REDACTED] worse than current product).
3. [REDACTED]  
[REDACTED].
4. Pant fit images will be investigated by an expert grader to identify any application errors (e.g., applied wrong way) [REDACTED]

5. Images of the wet stain on the overnight pajama pant will help identify the size of the stain and where the pant was leaking. This will be compared with the pant fit images.

## Skin Health

6. Parental skin rash perception (none/mild/moderate/severe). We will calculate the cumulative number of [REDACTED] scores [REDACTED]

[REDACTED]  
[REDACTED]  
[REDACTED].

[REDACTED]  
[REDACTED]  
[REDACTED]  
[REDACTED]  
[REDACTED].

[REDACTED]  
[REDACTED]  
[REDACTED]  
[REDACTED]  
[REDACTED].

[REDACTED]  
[REDACTED]  
[REDACTED]  
[REDACTED].

10. Skin irritation perception from child (burning/itching/ stinging/tingling/feeling of heat). We will calculate the cumulative number of skin irritation scores [REDACTED]

[REDACTED]  
[REDACTED]  
[REDACTED].

[REDACTED]  
[REDACTED]  
[REDACTED]  
[REDACTED]  
[REDACTED].

[REDACTED]

[REDACTED]  
[REDACTED]  
[REDACTED].

**Protocol Amendment I  
CSD2021096/ NCCI #12-2103**

**OVERNIGHT PANT SAFETY-IN-USE DIARY CLINICAL TRIAL FOR CHILDREN WITH NOCTERNAL  
ENURESIS**

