### 3.3.3 Compliance and Habits & Practice Questions

The following questions will be asked twice daily (am/pm) [REDACTED]:

1. Did your child experience any of the following health conditions since you last completed the questionnaire: diarrhea, fever, other illness, injury, or none of the above?
2. Has your child taken, or did you apply any of the following since you last completed the questionnaire: vaccination, medication, or none of the above?
3. Did your child bathe since you last completed the questionnaire?
4. Did your child swim since you last completed the questionnaire?
5. Did you or your child use cosmetics in the pant area since you last completed the questionnaire (lotion, oil, cream, powders, sunscreen, moisturizing bath additives, wet wipes, etc.)?
6. Which pants did you use since you last completed the questionnaire?

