### **3.5.2 Replacement of Subjects**

If a subject drops out of the clinical trial, they will not be replaced, due to the short duration of the clinical trial.

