#### **7.5.1 Adverse Event and Adverse Device Effect Reporting**

[REDACTED] the parent/legal guardian will be asked twice daily about their child's health and medication intake. Based on the information provided, Sponsor and PI will determine if it is appropriate to record as an Adverse Event or Adverse Device Effect and will contact the parent/legal guardian for more information. Such an occurrence does not necessarily have to have a causal relationship with product use. Due to the nature of this clinical trial, skin irritation in the pant area (diaper rash) will not be documented as an Adverse Event or Adverse Device Effect given it is one of the end points of interest for the clinical trial. However, if a skin reaction occurs in the pant area which causes the parent/legal guardian to seek medical attention, outside the normal follow-up given to the child within the clinical trial, this will be documented and followed in the same manner as other Adverse Events or Adverse Device Effects.

[figure not shown]
The Investigator or designee will review each Adverse Event Report and complete the form based on the following decision charts:

*Chart 1: Categories of ADE and AEs*

Adverse events	Non-device-related	Device- or investigational procedure-related	
Non-serious	Adverse event (AE) a (3.2)	Adverse device effect (ADE) c (3.1)	
Serious	Serious adverse event (SAE) b (3.45)	Serious adverse device effect (SADE) (3.44)	
		Anticipated	Unanticipated
		Anticipated serious adverse device effect (ASADE) c (3.1, Note 1 to entry)	Unanticipated serious adverse device effect (USADE) (3.51)

a Includes all categories.  
b Includes all categories that are serious.  
c Includes all categories that are related to the device or the investigational procedure.

Chart 2: AE categorization flow chart

The Investigator or designee will review each Adverse Event Report and complete the form based on the following definitions:

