**Action Taken by Investigator:**

- None - no change in product usage
- Reduced/Interrupted - product usage reduced or temporarily interrupted
- Discontinued - product usage discontinued.

*Note: Actions taken by parent/guardian may be documented in General Comments.*

The Investigator will decide on a case-by-case basis as to whether any subject should be dropped from the clinical trial. If the Investigator(s) or subject decides to discontinue clinical trial participation, this should be documented and filed with the Sponsor within 72 hours. All adverse events and adverse device effects will be followed until resolution or until the Investigator deems it safe to discharge the subject.

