**Attachment B**  
**Statistical Analysis Plan**

**Study Populations**

The Intent-to-treat (ITT) population is defined as all subjects who experienced the application of the assigned study product. The Per Protocol (PP) population includes subjects in the ITT population who have no serious inclusion/exclusion violations, no serious continuance criteria violations, no serious concomitant medication violations, and high study product compliance. The ITT population will be used for the safety analysis. Analyses of the Per Protocol population will be done to better understand the data.

Prior to the statistical analysis, all data will be checked for accuracy, completeness, and compliance to the study protocol. Subject evaluations will be checked for compliance to the study protocol regimen and subjects will be assessed for compliance to the protocol inclusion/exclusion criteria. Additionally, investigator comments will be assessed for extraneous factors that could affect the usefulness of the subject's data. Non-evaluatable observations and the rationale, along with the method for handling the observations will be documented by the sponsor prior to analysis of the data.

Period and carryover effects will be evaluated for potential influence on the results. Means will be plotted by periods to understand these effects.

Summary descriptive statistics will be provided for all parameters. Ninety-five percent confidence intervals (CIs) will be constructed for all clinical assessments for each treatment code. Any data reported as 'unable to evaluate' will be treated as missing and excluded from the analysis.

The methods used for the analysis will include but not be limited to a variety of parametric and non-parametric statistical methods based on the distribution/characterization of the data.

The following endpoints will be investigated.

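### Do the rash and irritation totals in the SAP lack a denominator, so that the product with fewer completed assessments looks better?

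*Combined protocol and SAP*

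**What the plan says.** Two items under Skin Health in Attachment B are at issue.

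- Item 6: "Parental skin rash perception (none/mild/moderate/severe). We will calculate the cumulative number of". The next word, which would say which scores are counted, is redacted. So is everything after the word for scores.
- Item 10: "We will calculate the cumulative number of skin irritation scores". Several redacted lines follow directly.

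The leak endpoint, item 2 under Product Fit and Performance, has a legible denominator: "We will calculate the percentage of leaks from loaded pants only". Its comparison rule comes next and is itself partly redacted.

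The Study Populations text of Attachment B covers all endpoints. It provides descriptive statistics for every parameter, 95% confidence intervals by treatment code for the clinical assessments, and an evaluation of period and carryover effects with means plotted by period. It also requires that the handling of non-evaluable observations be documented before analysis. On missing entries it states: "Any data reported as 'unable to evaluate' will be treated as missing and excluded from the analysis".

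On timing, protocol sections 3.2.1 (item 11) and 3.2.2 (item 1) give 45 questionnaire days, the first two of them practice. Section 3.1 gives two periods of three weeks, with two practice days before official data collection. The schedule in section 3.2.5 puts Visit 2 three weeks after Visit 1. Protocol Amendment 1 (revised section 3.2.1) plans about 16 children in each sequence.

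**The concern.** An expected total is the rate per assessment times the number of assessments. Without a denominator, missed diaries on one product lower its total and make it look gentler. Several provisions leave room for unequal numbers. Use of a product may be cut back ("Reduced/Interrupted - product usage reduced or temporarily interrupted"), entries that cannot be evaluated are excluded, and on withdrawals section 3.5.2 says: "If a subject drops out of the clinical trial, they will not be replaced". The contrast with the leak percentage suggests an oversight.

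The stakes would be real. Under section 7.5.1, "skin irritation in the pant area (diaper rash) will not be documented as an Adverse Event or Adverse Device Effect", unless the parent seeks medical attention for it. Below that level the adverse event listing does not show ordinary rash, and the skin scores have to carry it.

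The calendar adds to the doubt. If the practice days fall inside the first three weeks, period 1 has 19 evaluable days and period 2 may have 24.

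**Working it through.** The plan states no figure to reproduce: section 4.2 says that the sample size was set by practical limits. The check therefore has three parts.

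**1. What the text supports.** Items 6 and 10 break off at the same point. Item 2, which is more legible, gives the measure first and the comparison rule second. If items 6 and 10 follow that order, a denominator or rule would stand in the redacted lines. Redacted text is not missing from the plan, and no legible sentence makes raw totals the basis of the product comparison.

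**2. What the design gives by itself.** Inputs: 32 children, about 16 per sequence (Amendment 1); 45 questionnaire days, 2 of them practice (sections 3.2.1 and 3.2.2); two periods of 21 days (section 3.1).

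- Calendar: 2 practice + 21 + 21 = 44 nights. A diary that opens on the evening of day 1 and closes on the morning of day 45 covers exactly 44 nights.
- Questionnaires: 45 × 2 = 90. Day 1 has no morning entry and day 45 no evening entry, which leaves 88. Two practice nights take 4, leaving 84 = 2 × 42.
- On this reading the 45 days, the practice days and the two 3-week periods agree, and the Visit 2 timing is approximate.

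Let a and b be the evaluable days in periods 1 and 2, with m children test-first and n own-first. Test days = m·a + n·b and own days = m·b + n·a. At equal true rates, the ratio of raw totals equals the ratio of these two figures.

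| Reading | a | b | 16/16 | 15/17 | 14/18 |
|---|---|---|---|---|---|
| Practice first, then 21 + 21 | 21 | 21 | 672/672 = 1.00 | 1.00 | 1.00 |
| Practice first, then 21 + 22 | 21 | 22 | 688/688 = 1.00 | 689/687 = 1.003 | 690/686 = 1.006 |
| Practice inside first 21, then 21 | 19 | 21 | 640/640 = 1.00 | 642/638 = 1.006 | 644/636 = 1.013 |
| Practice inside first 21, then 24 | 19 | 24 | 688/688 = 1.00 | 693/683 = 1.015 | 698/678 = 1.029 |

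Unequal periods produce a period effect. At the planned split they produce no product effect. Even if four children were lost from one sequence under the 19/24 reading, the ratio would be 592/612 = 0.97 (16/12) or 612/592 = 1.03 (12/16).

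**3. What a material distortion would need.** The documents give no missing-data or dropout rates, so these are assumptions, with equal true rates on both products:

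- Missing 10% on test and 5% on own: 0.90/0.95 = 0.95. Missing 20% and 10%: 0.80/0.90 = 0.89. Missing 30% and 10%: 0.70/0.90 = 0.78. With the products swapped: 1.06, 1.13 and 1.29.
- Three of 16 test-first children leave after period 1, at 42 assessments per child and product: 1344/1218 = 1.10. Three own-first children leave instead: 1218/1344 = 0.91.
- Two leave from each sequence: 1260/1260 = 1.00.

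These ratios do not depend on how many scores a day yields. That number differs between the items: the endpoint table in section 3.1 times the child's irritation report just before pant removal, whereas section 3.3.4 lists rash twice daily in four regions.

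**The case for a change.** The strongest counter-argument is that the general SAP text does not settle the measure. A mean or a confidence interval of per-child totals still depends on how many assessments each child completed, and dropping entries that cannot be evaluated lowers a total without adjusting for it. The ITT definition can also include children with data on one product only. All of this is correct. If the unredacted items compared raw totals and completion differed by product, the comparison would be distorted as computed above.

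Both conditions are open, though. The first cannot be tested on the public text. The second has no figure behind it: the list of investigator actions and the no-replacement rule say what may happen to a child, not that one product will lose more assessments than the other. The plan also works against such loss, with at least weekly contact that covers missed questionnaires (section 3.2.2, items 8 and 9), remote compliance checks (section 7.4.1) and an evaluability meeting on data with coded products (Amendment 1).

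A per-assessment rate would not be a full cure either. If children stop because of rash, the rate is biased too. Should a rate be wanted, the data are there: section 3.3.3, item 6 asks "Which pants did you use since you last completed the questionnaire", so completed assessments can be counted by product.

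**Conclusion.** No defect is shown. The legible parts of items 6 and 10 name a running total and then stop at a redaction. An absent denominator cannot be inferred from that, nor can a comparison of raw totals. Under the planned crossover with 16 children per sequence, the product ratio of assessment days is 1.00 on every reading of the calendar, and it stays within about 3% at a 14/18 split. The calendar wording could be tidier, but on the natural reading it adds up and it changes no product comparison.

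Distortions of roughly 5% to 29% appear only under assumed differential missingness or one-sided dropout, combined with an assumed raw-total comparison. This conclusion rests on the redacted lines not prescribing such a comparison. The sponsor can confirm that from the full SAP, and it is a question rather than a fault in the plan.

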**Rationale for amendment:**

1. Correction of mistake in exclusion criteria. List of medication examples are mentioned in EXCL 2, but should be listed in EXCL 3.
2. Clarification of blinding of sponsor. Blinding of the sponsor representatives will be very difficult, due to the diary question about what product they used and the photos. Therefore the CTMs and DM cannot be fully blinded when they download the data, but all attempts will be made to blind the statistician and clinical scientist until after the database was locked. Also data for the evaluability meeting will be blinded by coding the options Own product and test product.
3. Include stratification criteria into the protocol.
4. Update the number of subjects enrolled to 32 instead of 30.

**Amended Protocol Sections for #1:**

**3.5.3 Exclusion Criteria**

**Original Wording:**

**EXCL02:** Does your child currently have (or have a history of) any significant illness or chronic medical condition (SITE: that in the opinion of the investigator may negatively impact child's health and/or clinical trial results, **for example medications to treat nocturnal enuresis, antibiotics, antihistamines, anti-inflammatory medications, corticosteroids, medications to treat yeast infection or similar**)?

**EXCL03:** Is your child currently using any medications? (SITE: that in the opinion of the investigator may negatively impact child's health and/or clinical trial results)?

**Revised Wording:**

**EXCL02:** Does your child currently have (or have a history of) any significant illness or chronic medical condition (SITE: that in the opinion of the investigator may negatively impact child's health and/or clinical trial results)?

**EXCL03:** Is your child currently using any medications? (SITE: that in the opinion of the investigator may negatively impact child's health and/or clinical trial results), **for example medications to treat nocturnal enuresis, antibiotics, antihistamines, anti-inflammatory medications, corticosteroids, medications to treat yeast infection or similar**).

**Amended Protocol Sections for #2:**

**3.1 Clinical Trial Design**

**Original Wording:**

This will be a single center, single blinded (sponsor's team will be blinded to the product codes), randomized, cross-over, IRB-Approved, in-home clinical test design over 6 weeks, with two usage periods of 3 weeks each.

**Revised Wording:**

This will be a single center, single blinded (sponsor's statistician and substitute clinical scientist for the evaluability meeting will be blinded to the product codes), randomized, cross-over, IRB-Approved, in-home clinical test design over 6 weeks, with two usage periods of 3 weeks each.

**Amended Protocol Sections for #3:****3.1 Clinical Trial Design****Original Wording:**

The order of the NJ EU product and own product will be randomized.

**Revised Wording:**

The order of the NJ EU product and own product will be randomized. At the end of visit 1, subjects will be randomized according to the strata as follows: gender (M or F) and age (4-5 or 6-7).

**3.2.1 Visit 1 – Enrollment and Training (on Site)****Original Wording:**

5. Subjects will be randomized to one of two usage periods, either starting with their own current product or starting with test product.

**Revised Wording:**

5. Subjects will be randomly assigned to begin with either their own product or the test product per a stratified randomization plan that utilizes randomization strata based on child's sex (male or female) and age group (4-5 years or 6-7 years). Randomization will be done so approximately 50% (n=16) of subjects will begin with their own product and approximately 50% (n=16) of subjects will begin with the test product. Product sequence will be assigned from a computer-generated randomization program provided by the Sponsor. The sequence of numbers used for the randomization will be 3-digit consecutive numbers whose first digit will not be the same as the 4-digit sequence used for subject identification (e.g., 301).

**Attachment R: COVID or Weather Impact to Clinical Trial Procedures****3.2.1 Visit 1A – Enrollment (Virtual for Covid)****Original Wording:**

5. Subjects will be randomized to one of two usage periods, either starting with their own current product or starting with test product.

**Revised Wording:**

5. Subjects will be randomly assigned to begin with either their own product or the test product per a stratified randomization plan that utilizes randomization strata based on child's sex (male or female) and age group (4-5 years or 6-7 years). Randomization will be done so approximately 50% (n=16) of subjects will begin with their own product and approximately 50% (n=16) of subjects will begin with the test product. Product sequence will be assigned from a computer-generated randomization program provided by the Sponsor. The sequence of numbers used for the randomization will be 3-digit consecutive numbers whose first digit will not be the same as the 4-digit sequence used for subject identification (e.g., 301).

**Amended Protocol Sections for #4:****3.1 Clinical Trial Design****Original Wording:**

Up to 30 children (approximate split of 15 males and 15 females) who meet inclusion/exclusion criteria will be enrolled in the clinical trial.

**Revised Wording:**

Approximately 32 children (approximate split of 16 males and 16 females) who meet inclusion/exclusion criteria will be enrolled in the clinical trial.

**Attachment A : Informed Consent: Procedures**

**Original Wording:**

Approximately 30 children with nocturnal enuresis (bedwetting) at least once per week will participate in this clinical trial.

**Revised wording:**

Approximately 32 children with nocturnal enuresis (bedwetting) at least once per week will participate in this clinical trial.

